7.2.4 Participant follow-up

The follow-up will begin on the day after the index date.

The follow-up end date will be defined as the date of treatment period end, date of death, the end of the study period, start date of other treatment drug, or date of outcome onset whichever comes first. The date of death means recorded in SS-MIX2 as “date of death” or “death” in the hospital visit information summary or recorded in the DPC file as “death” in the discharge summary. If discrepancies in the date of death are found between SS-MIX2 and DPC, preference is given to the DPC data. If the date of death is missing in the DPC data, the missing information will be supplemented using the SS-MIX2 data, if available.

[figure not shown]
Switching of the medication from one treatment group to another (from tedizolid to linezolid group or vice versa) or an addition of the other medication will also be considered as a termination of the initial treatment, and patients will be censored on the day of termination of the initial treatment, which will be operationally defined as the start of another treatment per

| | |
|---|--|
| PRODUCT: MK-1986 | PROTOCOL/AMENDMENT VERSION NO.: 1986-047-00-V3 |
| REVOPS ID NO: NIS106696 EPIDEMIOLOGY NO.(PE STUDIES ONLY): EP08063.004 | NIR DRC APPROVAL DATE: NOVEMBER 25, 2025 |

the database. Note, the additional date (date when another medication is added) and the switching date (overlapping treatment date) are included in the follow-up period.

Note, the previous feasibility study shows the median time to discontinuation of initial treatment as **CC1** days.

Figure 2: Follow-up Schema

a. the treatment period end, date of death, the end of study period, start date of other treatment drug, date of outcome onset, whichever comes first.

7.2.5 Longitudinality

This is a longitudinal surveillance. Factors to be considered in describing the clinical course of each patient are as follows:

1. All patients must have 60 days history before the index date (Lookback period).
2. The treatment period (continuous prescription period) for the tedizolid and linezolid groups is defined as from the index date to the end date of the last prescription period + grace period - 1.

A prescription period will be defined as prescription date + number of day's supply - 1.

| | |
|---|--|
| PRODUCT: MK-1986 | PROTOCOL/AMENDMENT VERSION NO.: 1986-047-00-V3 |
| REVOPS ID NO: NIS106696 EPIDEMIOLOGY NO.(PE STUDIES ONLY): EP08063.004 | NIR DRC APPROVAL DATE: NOVEMBER 25, 2025 |

The gap period is defined as the period from the end of the prescription period to the start of the next prescription period.

If the gap period is <14 days, the prescription periods are considered to be continued, and the prescription periods are consolidated. If the gap period is ≥ 14 days, the prescription periods are not consolidated, and the prescription periods after the gap period are not included in the analysis.

The gap periods for primary analysis are set at 14 days for tedizolid and linezolid based on the results of the feasibility study. It showed that the median gap period in the 1st use was [redacted] days for tedizolid group and [redacted] days for linezolid group. However, an analysis with a gap period of 7 days was also conducted as a sensitivity analysis (see Section 7.8.3 (3)). In addition, the feasibility study showed that the percentage of injections used was quite high (55/62 (88.7%) for tedizolid group and 476/574(82.9%) for linezolid group). Since most of the medication was injectable, the possibility of residual medication was considered to be low, and unnecessary to set a gap period longer than 14 days. In this study, this definition will be used as a common definition for tablets and injections. Also, it was considered unnecessary to set different treatment periods for injectable and oral agents.

The grace period is defined as the duration during which the effects of the drug may still be present, considering residual medication. It is considered the period that is added to the end date of the last prescription period. In this study, the grace period is set to be the same length as the gap period.

7.3 Variables

7.3.1 Exposure

The group of patients who are newly prescribed/exposed to tedizolid during the cohort entry period (21-Aug-2018 to 31-Mar-2025) will be considered as the tedizolid group. The start date of the cohort entry period coincides with the date tedizolid was placed on the market, so the index date corresponds to the new incident use of tedizolid in the database. The group of patients who newly start linezolid during the cohort entry period (21-Aug-2018 to 31-Mar-2025) will be considered as the linezolid group.

Patients will be considered as being exposed to the medication if there is a record for drug supply, i.e., prescription or dispensation record. Each prescription or dispensation will initiate a new prescription period that ends after the drug supply runs out. Also, a gap day between two prescription / dispensation records will be considered as a continuous prescription period if it is below the gap period.

7.3.2 Outcomes

The outcomes of interest in the study are peripheral neuropathy and optic nerve disorder.

Peripheral neuropathy is defined as cases meeting the following two conditions.

| | |
|---|--|
| PRODUCT: MK-1986 | PROTOCOL/AMENDMENT VERSION NO.: 1986-047-00-V3 |
| REVOPS ID NO: NIS106696 EPIDEMIOLOGY NO.(PE STUDIES ONLY): EP08063.004 | NIR DRC APPROVAL DATE: NOVEMBER 25, 2025 |

1. A confirmed diagnosis of peripheral neuropathy (ICD-10 code).
2. In the same month as, the month prior to, or the month after the confirmed diagnosis of peripheral neuropathy, a treatment drug for peripheral neuropathy or pain was prescribed, a test related to peripheral neuropathy was performed, or blood purification therapy for immune neuropathy was performed.

Optic nerve disorder is defined as cases meeting the following two conditions.

1. A confirmed diagnosis of optic nerve disorder (ICD-10 code).
2. In the same month as, the month prior to, or the month after the confirmed diagnosis of optic nerve disorder, vitamin B12 or corticosteroids were prescribed, or any of the relevant tests for optic nerve disorder (general, outpatient, or imaging tests) were performed.

The first event that meets any of the above definitions will be used for the analysis. The outcome occurrence date will be the earliest of the following: for Peripheral neuropathy, the prescription date of treatment drugs, the implementation date of blood purification therapy, or the test date; for Optic nerve disorder, the prescription date of treatment drugs or the test date.

Sensitivity analysis with variations of the about outcome definition regarding tests and treatment is detailed in Section 7.8.3 (7).

Although previous studies used ICD-9 codes to investigate peripheral neuropathy or ischemic optic neuropathy (7, 8), the codes identified in the literature might not be specific to the outcome in this study. Also, since there are no established diagnostic guidelines in Japan for peripheral neuropathy and optic nerve disorders, these definitions were established based on Japanese medical textbooks (9, 10) and Merck Manual Professional Version (11-15).

In addition, the above definition has been confirmed by medical doctor, and since there may be cases where tests and treatment drugs are not administered, an analysis using only diagnostic codes will be performed as a sensitivity analysis (see section 7.8.3 (8)).

However, it is important to note that low number of patients with these dx codes in feasibility assessment (There was no 1st user of tedizolid had dx for peripheral neuropathy and optic nerve disorder in the 90-day lookback period).

[Data components used for capturing the outcome]

- Diagnosis will be captured using ICD-10 code or receipt code from diagnostic information (illness order) of SS-MIX2 or DPC diagnostic information of DPC data or receipt diagnostic information of administrative claims data.

| | |
|---|--|
| PRODUCT: MK-1986 | PROTOCOL/AMENDMENT VERSION NO.: 1986-047-00-V3 |
| REVOPS ID NO: NIS106696 EPIDEMIOLOGY NO.(PE STUDIES ONLY): EP08063.004 | NIR DRC APPROVAL DATE: NOVEMBER 25, 2025 |

- Prescription of therapeutic drugs will be captured using the ATC code or receipt code from prescription / injection order of SS-MIX2 or prescription / injection of SS-MIX2 or DPC drug information of DPC data or receipt drug information of administrative claims data.
- The test will be captured using the receipt code from DPC medical practice information of DPC data or receipt medical care information of administrative claims data.

The code list for outcome definition is in Appendix A.

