7.5 Study Size

The incidence of adverse events related to peripheral neuropathy and optic nerve disorder in the international Phase III clinical trials (Studies TR701-112 and 113) was 1.2% (8/662 patients) and 0.3% (2/662 patients), respectively. Based on this consideration, the incidence of an event in the tedizolid was assumed to be 0.3% to 1.2%.

[figure not shown]
Based on the results of the feasibility study, the median continued prescription period for tedizolid was **CCI** days, with a 75% tile of **CCI** days. From the above, a follow-up period of about 30 days was assumed.

According to the results of the MID-NET survey, there were **CCI** cases of patients prescribed tedizolid with confirmed diagnosis of MRSA during the period from May 2018 to March 2025. Considering the loss of cases due to exclusion criteria, it is estimated 100-200 patients will be included in the study.

Under this assumption, the power is shown below (Fig. 3) when the risk ratio (rate ratio) is set between 1.2 and 5.0 and the sample size of the tedizolid group is varied in 20 increments from 100 to 200 of the predicted accumulation. Note that sample size of the control group (linezolid) was assumed to be approximately 10 times that of the tedizolid group. A generalized linear model assuming Poisson distribution was used to detect group differences.

Figure 3: Power at each sample size assuming an event incidence rate of 1.2% and a risk ratio of 1.2-5 in the tedizolid group

| | |
|---|--|
| PRODUCT: MK-1986 | PROTOCOL/AMENDMENT VERSION NO.: 1986-047-00-V3 |
| REVOPS ID NO: NIS106696 EPIDEMIOLOGY NO.(PE STUDIES ONLY): EP08063.004 | NIR DRC APPROVAL DATE: NOVEMBER 25, 2025 |

For each condition, there was no sample size required for Power to be greater than 80%.

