7.8.2 Primary objective

Incidence rates of peripheral neuropathy and optic nerve disorder and binomial confidence intervals will be calculated descriptively for tedizolid and linezolid groups separately. The number and percentage of patients with peripheral neuropathy and optic nerve disorder will be calculated. For all patients, the exposure time starts the day after the initiation of treatment date.

If there are 10 or more events observed for each treatment group, crude odds ratios and 95% CI will be estimated to be using logistic regression models, to compare the risk of peripheral neuropathy and optic nerve disorder between the tedizolid group and linezolid group (16).

Inverse probability of treatment weighting (IPTW) approach will be used to adjust for potential confounding between the tedizolid and linezolid groups (17,18). PS will be generated using probability estimates from a logistic regression model in which treatment with tedizolid or linezolid will be the binary dependent variable and patient characteristics (see Section 7.3.3) will be used as predictors of being treated with tedizolid or linezolid, if 10 patients exposed to tedizolid are observed per predictor. The IPTW approach uses weights derived from the PS to create a pseudo-population such that the distribution of baseline covariates in the population is independent of treatment assignment. For each patient, the weight will be assigned as the inverse of the propensity score for the tedizolid group and as the inverse of 1 minus the propensity score for the linezolid group will be calculated. The balance of baseline covariates will be assessed by using standardized mean differences; covariates will be well-balanced if the standardized mean difference is <0.1 (19,20). The distribution and variance for continuous variables will also be assessed between the treatment groups (20). Once balance of the covariates is achieved across the two treatment groups, the average difference in the risk of peripheral neuropathy and optic nerve disorder between the two treatment groups will be estimated using logistic regression models accounting for variance estimation (e.g., robust variance estimator) (21).

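### Read literally, the first-event rule leaves an optic nerve disorder that follows peripheral neuropathy (or the reverse) uncounted; the protocol should fix first event and end of follow-up per outcome

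*Protocol*

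**What the plan says.** Section 7.3.2 of the protocol opens with "The outcomes of interest in the study are peripheral neuropathy and optic nerve disorder". It gives one two-part definition for each, and then the rule: "The first event that meets any of the above definitions will be used for the analysis". It goes on to say how the onset date is set for each outcome. Section 7.8.3 repeats the rule under sensitivity analyses (7) and (8).

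Section 7.2.4 gives each patient one end of follow-up. The list of stopping events closes with "start date of other treatment drug, or date of outcome onset whichever comes first", and the note to Figure 2 says the same. Neither mentions a separate end date for each outcome.

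On reporting, Section 7.8.2 says: "The number and percentage of patients with peripheral neuropathy and optic nerve disorder will be calculated". Rates and, with at least ten events in each group, odds ratios are planned in similar terms. Section 7.5 cites the two outcomes with different incidences from the international Phase III trials: the incidence "was 1.2% (8/662 patients) and 0.3% (2/662 patients), respectively". The word composite appears nowhere.

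**The concern.** With one definition per outcome, a rule that takes the first event meeting any definition naturally runs across the two outcomes. Add a single end of follow-up, and a patient with neuropathy on day 8 and optic nerve disorder on day 15 contributes the neuropathy only, because observation stops on day 8.

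An optic nerve percentage built on this rule would estimate the risk of optic nerve disorder occurring first. The primary objective speaks of the risk of the outcome itself. The two differ whenever some patients have both. Overlap may exceed chance: the two are studied as possible effects of the same drugs, and Section 5 itself links optic nerve disorder to neuropathy in patients given linezolid. Optic nerve disorder is the rarer outcome, so it has the least room to lose an event. The rule also does not say what happens when both outcomes are dated to the same day.

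**Working it through.** **The text.** In Section 7.3.2 alone, the sentence could be a shorthand written once for both outcomes and meant for each. Section 7.8.3 (8) narrows that. There each outcome has a single condition, a confirmed diagnosis, yet the sentence again refers to any of the definitions. No alternatives exist within either outcome for it to choose among, so its plain meaning spans both. Section 7.2.4 offers no per-outcome follow-up to set against this, and no section provides for counting a second outcome of the other type.

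**The plan's own figure.** Section 7.5 reports that no tedizolid sample size considered gives power above 80%. Its setting is 1.2% in the tedizolid group, a linezolid group ten times as large, and "when the risk ratio (rate ratio) is set between 1.2 and 5.0". The most favourable case is n = 200 with a ratio of 5. Two-sided alpha of 0.05 is assumed, since the protocol gives none.

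- Expected events: tedizolid 200 × 0.012 = 2.4; linezolid 2000 × 0.012/5 = 4.8.
- Power = Φ(ln 5 / √(1/2.4 + 1/4.8) − 1.96) = Φ(1.609/0.791 − 1.96) ≈ 0.53.

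The statement reproduces. The present point disputes no stated figure and concerns only how events are counted.

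**Inputs for the counts.** All are from Section 7.5: neuropathy 1.2%, optic nerve disorder 0.3%; for tedizolid, "it is estimated 100-200 patients will be included in the study"; and "sample size of the control group (linezolid) was assumed to be approximately 10 times that of the tedizolid group", hence 1000-2000. Equal risks in the linezolid group are an assumption.

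**Expected events if each outcome is followed to its own onset** (n × risk):

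- Tedizolid: neuropathy 1.2-2.4; optic 0.3-0.6.
- Linezolid: neuropathy 12-24; optic 3-6.

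**Expected patients with both outcomes.** These are the only patients in whom a second event can be lost.

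- Independence, n × 0.012 × 0.003: tedizolid 0.0036-0.0072; linezolid 0.036-0.072.
- Full overlap (every optic case also has neuropathy), n × 0.003: tedizolid 0.3-0.6; linezolid 3-6.

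The full-overlap figures are ceilings. Optic events are lost on that scale only if neuropathy is also dated first every time. The documents give neither the overlap nor the usual order, so the range stays open between the two bounds. If tedizolid's risk were instead 1.2 to 5.0 times that of linezolid, the linezolid ceiling would run from 3/5 = 0.6 to 6/1.2 = 5.

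**Will the comparison run?** Sections 7.1 and 7.8.2 require ten events in each group. The binomial probability of at least ten tedizolid events at n = 200 is:

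- optic only, 0.3%: about 8 × 10⁻¹⁰;
- neuropathy only, 1.2%: about 0.0002;
- either outcome with no overlap, 1.5%: about 0.001.

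At the protocol's own risks, the descriptive counts will be the main result.

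**The case against.** The strongest defence is that the authors meant the first event for each outcome. Section 7.3.2 names two outcomes and gives separate dating rules for them straight after the disputed sentence. Outcome onset in Section 7.2.4 can be read as onset of whichever outcome is under analysis. A statistical analysis plan that is not shown may say so. This intent is possible, but the protocol does not state it, and Section 10 ties publications to the analyses specified in this protocol. The wording therefore needs correcting on either reading.

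A second defence is that harm needs two things together: a first-event rule across outcomes, and separate reporting of optic nerve disorder. If a combined event was intended, no separate optic percentage exists to be distorted. That is fair. Section 7.8.2 does not say whether the two outcomes are reported apart or together; the word separately there refers to the drug groups. A combined event would, however, have to be declared.

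Two stronger readings are tempting, and the documents do not support them.

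- A reader might infer that the study is sized for each outcome. Section 7.5 turns the two incidences into one range of 0.3% to 1.2% for an event, and the title of Figure 3 refers to 1.2% only.
- A reader might infer that the rule will make a harmful drug look safer for the eye. An optic nerve odds ratio is practically unreachable under the ten-event condition. The order of events is also unknown: pain drugs can date neuropathy early, but corticosteroids, vitamin B12 or general and imaging tests can equally date optic nerve disorder early.

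**Conclusion.** The point holds as a defect of wording with a small expected effect. Taken literally, Sections 7.3.2, 7.2.4 and 7.8.3 (7)-(8) leave a second outcome of the other type uncounted, while the protocol names two outcomes and declares no composite. Any outcome-specific figure would then be a first-event risk.

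For tedizolid, the drug under study, fewer than one patient with both outcomes is expected even at the ceiling. The linezolid ceiling of 3-6 rests on equal risks and complete overlap, and losing that many optic events also requires neuropathy always to come first. What remains exposed is the descriptive optic nerve count, where so few events are expected that one hidden event would be visible in the result. It would go too far to say that optic events will certainly be lost, since a per-outcome intent cannot be excluded. Severity is minor to moderate; this is not a fault that must be cured before the study can proceed.

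**What to change.** In Sections 7.3.2, 7.2.4 and 7.8.3 (7)-(8), state that peripheral neuropathy and optic nerve disorder are followed and analysed separately. For each outcome, the first event meeting that outcome's definition is used, and follow-up for that outcome ends at its own onset only; the other reasons for ending follow-up are unchanged. This also settles events of both types on the same date. If a combined first event is wanted, declare it and report it as an additional row. Say at the same time whether the ten-event condition in Section 7.8.2 applies to each outcome or to the combined event.

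The cost is a few sentences of protocol text and one follow-up variable per outcome in the programs. No further data or patients are needed.

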7.3.3 Covariates

The following variables for characterizing the study population will be collected and summarized:

- Demographics (age, sex)
- Year of prescription starts
- Severity of MRSA (pneumonia, sepsis, renal failure, dialysis, other anti-MRSA treatment)
- Comorbidities (cancer, heart-related disease, liver-related disease, hypertension, diabetes mellitus, dyslipidemia, cerebrovascular disease)
- Treatment history (antitumor agents)

Among the above variables, those expected to be confounders at this stage are listed in Table 4, which will be considered for covariate adjustment in the analysis.

Table 4: Covariates list

| Name of the covariate | Decision category | Measurement origin date and period |
|--|---------------------|------------------------------------|
| Patient characteristics at the start of follow-up | | |
| Age | Continuous variable | Index date [0,0] |
| Sex | Male/Female | |
| Severity of MRSA | | |
| Renal failure | Yes/No | Lookback period |
| Comorbidities | | |
| Cancer | Yes/No | Lookback period |
| Liver-related disease | Yes/No | |
| Hypertension | Yes/No | |
| Diabetes mellitus | Yes/No | |

| | |
|---|--|
| PRODUCT: MK-1986 | PROTOCOL/AMENDMENT VERSION NO.: 1986-047-00-V3 |
| REVOPS ID NO: NIS106696 EPIDEMIOLOGY NO.(PE STUDIES ONLY): EP08063.004 | NIR DRC APPROVAL DATE: NOVEMBER 25, 2025 |

| Name of the covariate | Decision category | Measurement origin date and period |
|--------------------------|-------------------|------------------------------------|
| Cerebrovascular disease | Yes/No | |
| Treatment history | Yes/No | |
| Antitumor agents | Yes/No | Lookback period |

7.4 Data Sources

See Section 7.2.1.

7.4.1 Study Procedures

7.4.1.1 Forecasted schedule

See Section 4.

7.4.1.2 Schedule and rationale for the progress of the surveillance and the milestones for evaluating the obtained results or reporting to PMDA

If necessary, consider further activities and measures based on the results of this surveillance.

7.4.1.3 Additional measures that may be implemented based on the results of the drug safety monitoring activities and criteria for starting them

If necessary, consider further activities and measures based on the results of this surveillance.

7.4.1.5 Organizational structure

The organization is shown in Appendix B.

7.4.1.7 Record keeping

Appropriate documents shall be saved in accordance with the MSD GPSP SOP and various guidance related to MID-NET.

7.5 Study Size

The incidence of adverse events related to peripheral neuropathy and optic nerve disorder in the international Phase III clinical trials (Studies TR701-112 and 113) was 1.2% (8/662 patients) and 0.3% (2/662 patients), respectively. Based on this consideration, the incidence of an event in the tedizolid was assumed to be 0.3% to 1.2%.

[figure not shown]
Based on the results of the feasibility study, the median continued prescription period for tedizolid was **CCI** days, with a 75% tile of **CCI** days. From the above, a follow-up period of about 30 days was assumed.

According to the results of the MID-NET survey, there were **CCI** cases of patients prescribed tedizolid with confirmed diagnosis of MRSA during the period from May 2018 to March 2025. Considering the loss of cases due to exclusion criteria, it is estimated 100-200 patients will be included in the study.

Under this assumption, the power is shown below (Fig. 3) when the risk ratio (rate ratio) is set between 1.2 and 5.0 and the sample size of the tedizolid group is varied in 20 increments from 100 to 200 of the predicted accumulation. Note that sample size of the control group (linezolid) was assumed to be approximately 10 times that of the tedizolid group. A generalized linear model assuming Poisson distribution was used to detect group differences.

Figure 3: Power at each sample size assuming an event incidence rate of 1.2% and a risk ratio of 1.2-5 in the tedizolid group

| | |
|---|--|
| PRODUCT: MK-1986 | PROTOCOL/AMENDMENT VERSION NO.: 1986-047-00-V3 |
| REVOPS ID NO: NIS106696 EPIDEMIOLOGY NO.(PE STUDIES ONLY): EP08063.004 | NIR DRC APPROVAL DATE: NOVEMBER 25, 2025 |

For each condition, there was no sample size required for Power to be greater than 80%.

